8.1 General Conventions

Study data will be analyzed for all subjects in the Safety Analysis Set using SAS v9.3 or higher. Planned tabulations are described below and table, figure, and listing shells are provided separately.

Standard descriptive summaries for continuous data will include the number of subjects with non-missing data (n), mean, standard deviation (SD), median, minimum, and maximum values. For categorical data, counts and percentages will be provided. Percentages will be based on the number of subjects who do not have missing data for the respective endpoint.

¹ Cantor, A. Estimates of the Variance of the Kaplan-Meier Estimator. In: *Extending SAS® Survival Analysis Techniques for Medical Research*. 2nd ed., Cary NC: SAS Institute, 2003:24.

8.2 Disposition of Study Subjects

The number of study subjects, withdrawals before study completion, and those who have completed the study (All Safety Analysis Set subjects that were recorded to have completed the study requirements as outlined in the protocol) will be summarized.

8.3 Demographic and Baseline Characteristics

Descriptive statistics (at time of index surgery) will be displayed for subjects in the Safety Analysis Set:

- Age at time of index surgery (in years);
- Gender;
- Height;
- Weight;
- BMI (kg/m²);
- Ethnicity;
- Race;
- Any Known Allergies;
- Primary Diagnosis;
- Other Joint Involvement;
- General Medical Conditions;

8.4 Endpoint(s) and Associated Hypotheses

8.4.1 Primary Endpoint(s)

The primary endpoint of this study is device survivorship at 5 years post-op. A revision is defined as the removal of any THA component(s), and device survival is defined as the lack of revision. No hypothesis tests of the primary endpoint are planned.

8.4.2 Secondary Endpoints

The secondary endpoints of this study are Harris Hip total and sub-score means, radiographic evaluations, device survivorship annually through 5 years post-op, and adverse event outcomes at each protocol defined post-op interval. No formal hypothesis tests of the secondary endpoints are planned. Confidence intervals and p-values may be provided (such as for the Cox proportional hazards model) to facilitate clinical judgement.

8.4.3 Additional Endpoints

Questions pertaining to function, pain, plans for any upcoming revisions, and satisfaction with the index hip replacement procedure were asked of study subjects, some by telephone if telephone follow-up was utilized. Responses to these endpoints are considered to be exploratory endpoints and will be summarized.

8.5 Analysis of Primary Endpoint(s)

8.5.1 Plans for Interim Analysis

There were no planned interim analyses for the purpose of terminating the trial early. Interim analyses of the primary and secondary endpoints were carried out to provide interim PAS progress reports to the FDA.

8.5.2 Plans for Final Analysis

A Kaplan-Meier survivorship analysis will be provided, with device survivorship as a function of post-op time. Implant survivorship will be reported for each year where greater than 40 hips are still at risk of revision. The 5 year KM survivorship estimate is the primary endpoint analysis.

8.6 Handling of Missing Data

In the analyses of all primary and secondary endpoints, no missing data imputation methods will be implemented.

8.7 Safety Analyses

Adverse events which occurred during subjects' participation in this PAS will be summarized. Adverse Events will be coded according to Medical Dictionary for Regulatory Activities (MedDRA) version 14.0 or higher.

An overall summary of the AE incidence will be presented, broken down by systemic and surgical site, and will include the number and percentage of subjects having one or more:

- Serious adverse event (SAE)
- Operative Site AEs
- Systemic AEs
- Device related AEs
- Procedure related AEs

The number and percent of subjects with adverse events and the 95% binomial exact confidence interval for this percent will be presented by MedDRA system organ class (SOC) and preferred term (PT) for all AEs and stratified for systemic and operative site adverse events. A subject-level listing will be provided to display details of all AEs.

8.8 Analyses of Secondary Endpoints

Harris Hip score summary statistics and change from baseline statistics will be reported for each protocol defined post-op visit interval. These will be provided for total Harris Hip score as well as the Harris Hip sub-scores (pain, function, activity, deformity, and range of motion). Results will be presented overall, as well as stratified by obesity (non-obese vs. obese) according to BMI (subjects with $BMI < 30$ vs. subjects with $BMI \geq 30$, respectively). Responses to questions on the Subject Hip Outcomes questionnaire will be summarized at each post-op visit interval. Radiographic summaries will be provided for each protocol defined post-op visit interval. Device survivorship will be estimated at each year post-operatively. A proportional hazards model will be provided, in which device survivorship is a function of post-op time, and BMI (at the time of index surgery) is a covariate.

8.9 Additional Endpoint Analyses

All analyses which are described in sections 8.3, 8.5, 8.7, 8.8. will also be provided for the following subgroups:

- Each stem type (e.g., S-ROM, Summit, etc.) for which there are 10 or more subjects
- Each cup type (e.g. Pinnacle 100, Pinnacle Sector, etc.) for which there are 10 or more subjects

KM survivorship and cox proportional hazards models will only be conducted for subgroups which have more than 40 subjects.

9 Data Monitoring Committee (DMC)

A DMC was not used to monitor safety or efficacy in this study.

10 Appendix: Tables, Listings and Graphs Shells

A separate document will illustrate presentation for all planned Tables and Listings.

11 Reference(s)

¹ Cantor, A. Estimates of the Variance of the Kaplan-Meier Estimator. In: Extending SAS® Survival Analysis Techniques for Medical Research. 2nd ed., Cary NC: SAS Institute, 2003:24.

End of Document

Revision History for SAP Template

SUMMARY OF CHANGES	
Revision No.	Description of Change
1	New Document – Procedure Harmonization
2	Update role names for consistency across SOPs Added statement to randomization and blinding procedure section regarding a randomization plan Moved section related to primary and secondary endpoint analysis to be part of the analysis to be conducted section Added Safety Analysis section Added Adjustments for Multiplicity section Moved DMC section to bottom of template
3	Update approver to reflect 'Franchise Clinical Platform Lead' instead of 'Franchise Platform Head of Clinical Research' to reflect current structure
4	Updated footer to match version and added revision history table
5	Added company logo to the title page Require adding SAP template version in the history of revisions Added list of acronyms and abbreviations Replaced TOC with a working one Updated footnote to include version, confidential, and page number Added text to Introduction Made changes to the wording and order of section 8, which resulted in shifting of subsections Description added to Analyses of Secondary Endpoints Updated Appendix description and made it optional Added Reference section

Ceramax 12017 SAP FINAL 20DEC2023

Final Audit Report

2024-01-19

Created:	2023-12-20
By:	PPD
Status:	Signed
Transaction ID:	CBJCHBCAABAAaSjM7CygGzLXA63R2QR_IsSSOratqZOE

"Ceramax 12017 SAP FINAL 20DEC2023" History

-  Document created by PPD
2023-12-20 - 9:03:12 PM GMT- IP address: PPD
-  Document emailed to PPD for signature
2023-12-20 - 9:07:09 PM GMT

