7.3 PINNACLE Metal Outer Shell

The shells are designed to assemble to the ceramic insert components described above. The styles utilized in this clinical investigation are the POROCOAT-coated PINNACLE 100, PINNACLE 300, Sector II, and Multi-Hole Series shells.

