7.5 Femoral Stem

The stems with the 36 mm CERAMAX® device include the SUMMIT® POROCOAT®, Tri-Lock® Bone Preservation Stem (BPS) and the S-ROM® devices only. Refer to **Exhibit K** for a complete listing of permitted stems.

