8.3 Primary Endpoint Justification

The maximum acceptable hazard of revision for the COC 36 mm system is assumed to be a constant 1% per year, that is, $h(t) = 0.01$. The survival function for this hazard is

$$S(t) = \exp \left[- \int_0^t h(u) du \right] = \exp (-0.01t),$$

so at 5 years, a minimally acceptable level of survival is assumed to be

$$S(10) = \exp[-0.05] = 0.951.$$

It will be demonstrated that the Kaplan-Meier 5-year point estimate of survival is at, or higher than this minimally acceptable level of 95.1%.

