Interim Visits	
An interim office visit is defined as any visit at the study site where a study Subject is seen by one of the site staff including the Principal Investigator (PI), any sub-investigator (as appropriate), and anyone identified on the PI's team, outside of the scheduled study visit. An interim visit is only to be reported when the visit falls between study intervals as described in Table 4. An Interim Visit CRF is not to be completed if the Subject comes in for additional, unplanned visits in the "in-window" study interval.
 
If the previous protocol-defined, study interval visit was missed, the required CRFs in that previously-missed interval visit are also required along with the Interim Visit CRF.
 
If the interim visit is related to a new, worsening, or resolved adverse event, both an Adverse Event CRF and Interim Visit CRF are completed.

End of Study/ Withdrawal	
This form must be completed for all enrolled subjects to either reflect
 
 • Completion of final endpoint (Minimum 5 years) • Premature withdrawal 
Study participation may be prematurely discontinued through revision of acetabular components (shell and/or liner), withdrawal of consent, or death.
 
➤ NOTE: A revision is defined as a surgical procedure of the affected hip where one or more of the THA components (femoral stem, femoral head, acetabular shell and/or acetabular liner) are removed. Of note, if both the acetabular shell and ceramic liner remain intact, the Subject will continue to be followed in the study.
 
➤ NOTE: Should it be necessary for the Subject to undergo a revision of either the acetabular shell and/or the acetabular liner between the date of the enrollment and the completion of the study data acquisition, the Subject is withdrawn from study participation. Thus, both an Adverse Event (AE) CRF and an END of Study/Withdrawal CRF would be completed.

Electronic Case Report Forms (CRFs) entered into an electronic data capture (EDC) system will be used to collect all Subject data once a Subject is enrolled in the study. Study sites will be instructed to enter Subject data on to the CRFs via the EDC web-based database portal.

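### Should the subgroup BMI Cox models in SAP 8.9 be gated on revisions rather than on more than 40 subjects?

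*SAP*

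**What the plan says.** SAP 8.8 includes a proportional hazards model in which "device survivorship is a function of post-op time, and BMI (at the time of index surgery) is a covariate". It does not say whether BMI enters as a continuous variable or split at 30, the cut that the same section uses for Harris Hip scores.

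SAP 8.9 carries the 8.8 analyses into every stem type and cup type with at least 10 subjects, then limits the survival models: "KM survivorship and cox proportional hazards models will only be conducted for subgroups which have more than 40 subjects". Neither document sets a minimum number of revisions, overall or by subgroup. The other rule built on 40 (Protocol 8.9, SAP 8.5.2) counts hips still at risk and governs which years of the survival curve are reported.

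Protocol 8.9 promises these analyses in each interim report for every stem type and cup type represented. Protocol 7.5 allows three stem families: SUMMIT, "Tri-Lock® Bone Preservation Stem (BPS) and the S-ROM® devices only". Protocol 7.3 lists four shells: "The styles utilized in this clinical investigation are the POROCOAT-coated PINNACLE 100, PINNACLE 300, Sector II, and Multi-Hole Series shells".

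SAP 5 states that there are no pre-specified hypotheses and that everything is exploratory. SAP 8.4.2 leaves p-values and intervals for the Cox model optional. The only hazard in the documents is in Protocol 8.3: "The maximum acceptable hazard of revision for the COC 36 mm system is assumed to be a constant 1% per year".

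**The concern.** A head count suits a Kaplan-Meier curve, whose reliability at a given time depends on how many hips remain at risk. It does not suit a Cox model, where the variance of the log hazard ratio falls with the number of events. Revisions are rare here by design, so a subgroup can pass the gate with one revision or none. With none, the BMI hazard ratio cannot be estimated; with one or two, it is too imprecise to interpret. The worry is that such a hazard ratio is tabulated by stem or cup type in a report to FDA and read as if it carried information.

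**Working it through.** **Inputs.** Hazard 0.01 per year (Protocol 8.3); minimum enrolment 170 (SAP 7); smallest qualifying subgroup 41 (SAP 8.9); last visit window ends on day 2,555, about 7 years (SAP 4). Subgroup sizes are not in the documents. An equal split is an assumption: 170/3 = 56.7 per stem family and 170/4 = 42.5 per shell style. The size 85 is half of 170.

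**Reproducing the plan's figure.** S(5) = exp(−0.01 × 5) = 0.9512, which matches the stated 0.951 (printed under the label S(10)). The 5-year revision probability is p = 1 − 0.9512 = 0.0488.

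**Expected revisions, n × p, with binomial probabilities (full follow-up to 5 years).**

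| n | Expected revisions | Chance of fewer than 5 |
|---|---|---|
| 41 | 2.00 | 95% |
| 57 | 2.78 | 86% |
| 85 | 4.15 | 60% |
| 170 (overall model) | 8.29 | 8% |

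For n = 41 the chance of no revision is 0.9512^41 = 12.9%, and the chance of at most one is 39.9%.

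**Range for n = 41.**
- All followed for 7 years: 41 × (1 − exp(−0.07)) = 41 × 0.0676 = 2.77.
- 20% lost evenly by year 5 (assumption): loss rate c = −ln(0.8)/5 = 0.0446; event probability 0.01/(0.01 + c) × [1 − exp(−5(0.01 + c))] = 0.0438; 41 × 0.0438 = 1.79.
- Half the hazard (assumption): 41 × (1 − exp(−0.025)) = 41 × 0.02469 = 1.01, with a 36% chance of none.

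**Precision.** With d events, approximate 95% limits per standard deviation of BMI are the estimate multiplied or divided by exp(1.96/√d).
- d = 2: exp(1.386) = 4.0.
- d = 4: exp(0.98) = 2.7.
- d = 5: exp(0.877) = 2.4.
- d = 8.3 (overall model): exp(0.680) = 2.0.

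If BMI were coded obese against non-obese with a 50:50 split (assumption), the information is d/4 and the factors are exp(1.96/√0.5) = 16 for two events and exp(1.96/√1) = 7.1 for four. These are large-sample approximations and only indicative at such small counts.

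**What a minimum of, say, 5 revisions would do.**
- Subjects needed to expect 5 revisions: 5/0.0488 = 102.5, so 103 over 5 years; 5/0.0676 = 74 if all were followed for 7 years; 5/0.02469 = 202.5, so 203, at half the hazard.
- Since 2 × 103 = 206 exceeds 170, at most one stem type and one cup type could reach 103. At half the hazard none would be expected to qualify.
- The overall model would be exposed to the same rule: at half the hazard it expects 170 × 0.02469 = 4.20 revisions, with about a 59% chance of fewer than 5.

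**The case for a change.** The strongest case for a change is that an exploratory label does not stop a hazard ratio resting on one or two revisions from being tabulated, and the SAP makes even the interval optional. If BMI is entered per kg/m², the imprecision is also hard to see. A factor of 4.0 per standard deviation prints as 4.0^(1/SD): 1.41 for an SD of 4 and 1.26 for an SD of 6 (SDs assumed). The equal-split sizes of about 57 and 42 or 43 show that a subgroup near the gate is plausible.

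What stands is that a reader needs the revision count, the BMI coding and the interval to judge any of these hazard ratios. Whether they are already printed cannot be judged, because the table shells are in a separate document. The per-unit argument also depends on a continuous coding that SAP 8.8 does not state; with a split at 30, the limits would be visibly uninformative.

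The stronger remedies do not hold up:

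- **A minimum number of revisions.** No figure in the documents supports a particular cutoff, and 5 still leaves a factor of 2.4. Exempting the overall model would be inconsistent, and including it could remove that model too. SAP 3 says the sponsor was never blinded and SAP 8.5.1 says interim analyses were carried out, so a cutoff added now could be chosen with the counts known.
- **A different interval.** In a null simulation (n = 41, standardised normal covariate, 2,000 runs per event count), coverage at 1, 2 and 5 events was 100%, 98.2% and 95.4% for Wald limits and 91.4%, 93.2% and 94.1% for profile-likelihood limits. The 5% of one-event fits with no finite estimate were counted as covered for Wald. This gives no reason to prefer profile likelihood.
- **A listing of revisions in place of the model.** SAP 8.7 already promises this: "A subject-level listing will be provided to display details of all AEs". SAP 8.9 repeats it by stem and cup type, so only BMI would be new. One might fear that stem-only or head-only revisions would be missing. The endpoint counts them ("A revision is defined as the removal of any THA component(s), and device survival is defined as the lack of revision"), while the form instruction in Protocol Table 3 covers shell or liner revisions: "Thus, both an Adverse Event (AE) CRF and an END of Study/Withdrawal CRF would be completed". But Protocol Table 5 classes events needing inpatient admission, or surgery to prevent permanent impairment, as serious, and Protocol 10.5 requires all serious events on the adverse event form. A revision would ordinarily qualify whichever component is removed.

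**Conclusion.** The gate does count the wrong quantity for a Cox model, and subgroups that pass it may carry very few revisions: about 2 at 41 subjects (1.0 to 2.8 across the assumptions above) and about 4 at 85. These counts rest on the protocol's ceiling hazard, which is a maximum acceptable value and not a forecast; a better-performing device would give fewer. Actual subgroup sizes and revision counts are not in the documents.

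No change to the plan follows. The primary 5-year Kaplan-Meier estimate does not use these models, no hypothesis is tested, and no conclusion depends on a subgroup hazard ratio. For the Kaplan-Meier part, the gate is coherent with the at-risk reporting rule, because a subgroup of 40 or fewer could never meet it. Fitting the promised models and letting their intervals show how little they say is a fair trade-off against withholding them under an arbitrary rule set late. An analyst will report a model with no revisions as not estimable, and showing the number of revisions, the BMI coding and the 95% interval beside each hazard ratio is ordinary table content.
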